13.6 NOTIFYING HEALTH CANADA

For drugs used in clinical trials in Canada, only adverse drug reactions (ADRs) that are both serious and unexpected are subject to expedited reporting to Health Canada. Expedited reporting of reactions which are serious but expected is not required. Expedited reporting is not required for serious events from clinical investigations that are considered unrelated to the study product, whether or not the event is expected.

During a clinical trial the sponsor is required to inform Health Canada of any serious, unexpected adverse drug reaction that has occurred inside or outside Canada. ADR report must be filed in the cases:

- where the ADR is neither fatal nor life-threatening, within 15 days after becoming aware of the information
- where it is fatal or life-threatening, immediately where possible and, in any event, within 7 days after becoming aware of the information
- within 8 days after having informed Health Canada of the ADR, submit as complete as possible, a report which includes an assessment of the importance and implication of any findings

Each ADR which is subject to expedited reporting should be reported individually in accordance with the Health Canada / ICH Guidance Document E2A: Clinical Safety Data Management: Definitions and Standards for Expedited Reporting (77).

Ongoing safety information respecting a drug should be conveyed to Investigator(s) and their Research Ethics Board(s). For further information refer to the Health Canada / ICH Guidance Documents E6: Guideline for Good Clinical Practice and E2A: Clinical Safety Data Management: Definitions and Standards for Expedited Reporting.

A completed ADR Expedited Reporting Summary Form should be attached to the front of the completed ADR report (suggested ADR report format:  Suspect Adverse Reaction Report - CIOMS form of  the Council for International Organizations of Medical Sciences (CIOMS)).

All forms can be found on Health Canada's website and reports should be submitted by fax to the appropriate Directorate.

See Health Canada Website for more information: http://www.hc-sc.gc.ca/dhp-mps/prodpharma/applic-demande/guide-lid/clini/cta_post_approval-eng.php#adr

13.7 UNBLINDING PROCEDURE

An investigator whose participant experiences side effects can be un-blinded if knowledge of the participant treatment is necessary in order to deliver appropriate treatment.

Should any events occur during surgery, whereby, the surgeon or anesthesiologist feel it is necessary to unblind the treatment, a call will be placed to the hospital's pharmacist who will advise which treatment the patient is receiving and the patient will be treated medically as dictated by the event.

Should any events occur during the 5 day post-operative period, whereby it is felt that it is necessary to unblind the treatment, the patient's surgeon will be contacted and will make the final decision to unblind the treatment or not. Should the response be affirmative, a call will be

placed to the hospital's pharmacist who will advise which treatment the patient is receiving. There is no need to taper off the medication as the dosage given is very small.

If un-blinding occurs and medication is stopped immediately. No dose modifications will be made. The patient will be asked to remain in the study as we can still collect valuable information through blood samples, QST and questionnaires; however, no further medications or placebos will be given.

At the conclusion of the study, all investigators will be unblended with respect to their participant's treatments.

14 DATA HANDLING AND RECORD KEEPING

14.1 CONFIDENTIALITY AND SECURITY

Data handling and protection are in accordance with the guidelines of ICH-GCP and applicable regulations. Validated outcome measures are used. Data collection for this study will primarily be through an online data management system housed on SHC servers. Members of the SHC research team will enter data into SHC system with unique user IDs and passwords. All secure web-based information transmission is encrypted and complies with HIPAA security guidelines and 21 CFR 11.

14.2 QUALITY CONTROL AND QUALITY ASSURANCE

The PI is responsible for all data and specimen management of all aspects of the study. The PI and the study project coordinator will be responsible for evaluating the data and ensuring the study team adheres to the protocol. Monthly meetings with the research team will be held to review and ensure the data is accurate and complete.

Investigators, approved study staff, collaborators, Shriners Hospital for Children, Health Canada, and McGill University Institutional Review Board may review records for research, quality assurance, and data analysis.

14.3 DATA STORAGE

For this study, source data will be collected by way of paper data collection forms. Patient data will be de-identified and given a unique numerical identifier. Data from the questionnaires and the data collection forms will be transcribed into a password protected electronic database housed on a SHC-Canada server using only the unique identifiers. A separate patient study log will be kept by the Principle Investigator linking the unique identifier to the patient data. All study data and the patient study log will be stored in a locked filing cabinet in a locked office at the SHC-Canada located at [name]. Only authorized research personnel will have access to the documents and research computer.

14.4 CONFIDENTIALITY AND SECURITY

Privacy and confidentiality of the patient's medical data will be maintained through the study. Case report forms and all other documents pertinent to the study will be de-identified and carry only the numeric patient's identifier code. The site will maintain the link between the patient identifier code and the patient's names.

Personal medical information will at all times be treated as confidential. The informed consent document will contain information about the confidentiality of the medical information and approval for the access.

In the event that a subject revokes authorization to collect or use their personal medical information, the investigator, by regulation, retains the ability to use all information collected prior to the revocation of subject authorization.

14.5 SOURCE DOCUMENTATION

The following outcome measures will be used to collect data and will be considered source documents:

The above questionnaires are all considered source documents in addition to the following:

- ✓ The Faces Pain Scale – Revised (FPS-R)
- ✓ State-Trait Anxiety Inventory - (STAI-C)
- ✓ Pain Catastrophizing Scale (PCS)
- ✓ Functional Disability Index (FDI)
- ✓ Revised Children Anxiety and Depression Scale (RCADS)
- ✓ Pittsburgh Sleep Quality Index (PSQI)
- ✓ Neuropathic Pain Questionnaire (DN4)
- ✓ Tampa Scale for Kinesiophobia (TSK)
- ✓ Scoliosis Research Society Questionnaire- Quality of Life Tool (SRS-30)
- ✓ The Adolescent Pediatric Pain Tool (APPT)
- ✓ Patient's Global Impression (PGIC)
- ✓ Blood Sample Collection Form
- ✓ MDT/PPT Data Collection Form

- ✓ CPM Data Collection Form
- ✓ Surgical Data Collection Form
- ✓ Concomitant Medication Form
- ✓ AE & SAE Form
- ✓ Spinal Deformity Intra-Operative Monitoring Work Sheet (SDIM)
- ✓ Patient Home Interview / Phone Call Form

14.6 RECORD RETENTION

Source data, clinical data and other essential documents will be retained according to the SHC Standard Operating Procedure on Clinical Research Records Retention.

Study data will be kept for 25 years after the results have been published in a healthcare journal.

15 QUALITY CONTROL AND QUALITY ASSURANCE

15.1 DATA SAFETY MONITORING BOARD (DSMB)

An independent Data Safety Monitoring Board (DSMB) will be assembled. Composition and details of the DSMB will be compliant to Health Canada requirements and will be in place prior to the initiation of the study.

15.2 STUDY MONITORING PLAN

Monitoring Plan

Monitoring will occur at 3 time points in throughout the study; 1) After the first 10 patients have been recruited; 2) After half the study patients have been recruited; 3) At close of study.

Source Data Verification (SDV) of critical data will be performed all on all patients in the study. A minimum of 25% or 10 patients recruited at the time of the monitoring time point will undergo 100% SDV. Patients study numbers will be randomly drawn from a box.

Critical data is defined below:

- Informed consent
 - Signature and dated by patient
 - Signature and dated by person consenting the patient (study team)
 - Inclusion criteria met
 - Females* aged between 10 and 21 years old

- Scheduled to undergo posterior spinal fusion surgery for AIS with instrumentation
- Ability to adequately understand and respond to outcome measures
- No previous major orthopedic surgery
- Exclusion criteria met
- Children with history of myocardial disease, arrhythmias, cerebrovascular disease, Raynaud's/Thromboangiitis obliterans or chronic renal failure
- Children taking antihypertensive agents (diuretics, vasodilators, beta-blockers, ace-inhibitors)
- History of depression
- Inability of the child to speak English or French
- Diagnosed with developmental delay that would interfere with understanding questions being asked (autism, mental retardation)
- Children with major chronic medical conditions (ASA status III or higher)
- Pregnancy
 - Verification that all QST was completed
 - Verification that study medications were taken as per protocol

100% Source Data Verification

- Verification of medical records for AE and SAE occurrence
- Verify and compare all data collected to medical records and worksheets

If unreported AEs, SAEs or SDRs are found in any study files, the study files of the 3 consecutive patients will undergo 100% SDV.

16 STATISTICAL CONSIDERATIONS

16.1 PRIMARY STUDY ENDPOINTS

Average pain intensity over the past 7 days (0–10 numerical rating scale where 0 indicated “no pain” and 10 “worst possible pain”) six weeks and six months after surgery [73].

16.2 SECONDARY ENDPOINTS

Chronicity of postsurgical pain: Six months after surgery, CPSP will be defined in a dichotomous way (yes/no) as the presence of symptoms 6 months after surgery is reported.

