1 INTRODUCTION & BACKGROUND

Thousands of children undergo surgery across the Shriners system each year. These children are at a particularly high risk of suffering significant pain as many of the orthopedic surgical procedures are invasive. Under-treated postoperative pain in children leads to increased postoperative morbidity [1] and can have a negative impact on all aspects of health related quality of life including physical (e.g., reduced quality of sleep, delayed mobilization), emotional (e.g., anxiety, distress, negative thoughts), reduced social interactions with friends and family and school absenteeism [2]. Postoperative pain has immediate consequences leading to postoperative morbidity [1] Moreover, between 10 to 20 % of children undergoing surgery will develop chronic postsurgical pain (CPSP), making this problem the most common surgical complication [3,4]. Preventing CPSP becomes highly relevant as it may predispose children to experience recurrent pain during adulthood [5,6]. The clinical challenge rests in the ability to determine which patient will be at risk of having poor postoperative pain control and the development of CPSP. The challenge is even more relevant as to which analgesic protocol will best relieve pain for a specific patient. In this context, it is of high relevance to provide clinicians a tool to identify patients at risk of having poor postoperative pain control and CPSP. Ideally the tool should provide a rational (physiological/mechanistic based) approach to the establishment of a personalized analgesic perioperative protocol.

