4 PRELIMINARY DATA AND CLINICAL DATA

In a previous study, we have demonstrated that presence of pain before surgery was the best predictor of pain intensity after surgery in Adolescent Idiopathic Scoliosis (AIS) patients undergoing surgery [30]. Pain before surgery was reported by 48% of the cohort (n=50) (Figure 1). We also demonstrated that intensity of pain in the first days after surgery was associated with pain intensity weeks after surgery, thus demonstrating the clinical need to improve preoperative and acute pain management in order to minimize long-term consequences.

Figure 1. Patients reporting preoperative pain had greater postoperative pain intensity levels during the first postoperative 24 hours (POD1, $r=0.47$, $p=0.001$) (A), the second 24 hours (POD2, $r=0.35$, $p=0.025$) (B) and at follow-up appointment (4-6 weeks after surgery, $r=0.50$, $p<0.001$) (C). The pain intensity during POD1 was also predictive of the pain intensity during POD2 ($r=0.74$, $p<0.001$) (D) and at follow-up (6 weeks post-surgery, $r=0.43$, $p=0.005$) (E) (Ferland et al. 2016, PMID: 26852092).

In the same cohort, we also quantified neurotransmitters known to be related to pain. The preoperative plasma levels of norepinephrine metabolite metanephrine concentrations revealed to be associated with the postoperative pain intensity (Figure 3). Although preliminary, these results suggested that preoperative inter-individual differences, could explain postoperative pain trajectories.

[figure not shown]
[figure not shown]

[figure not shown]
Figure 2. Preoperative monoaminergic levels on postoperative pain intensity. The preoperative metanephrine plasmatic levels of AIS patients scheduled for surgery. Patients who reported greater pain intensity at 6 weeks after surgery had higher metanephrine plasmatic levels before surgery (n=50, $P<0.001$) (Ferland et al., manuscript in preparation).

In the largest study to examine longitudinal pediatric pain trajectories after spine surgery, Sieberg et al proposed perioperative trajectories of pain experience may be better explained by changes in the central pain modulation rather than in the surgical stimulus itself (Figure 3).

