8.2 RECRUITMENT

Patients will be recruited from outpatient clinics at the Shriners Hospital for Children - Canada. Potential participants will be identified and informed of the study by their attending physician at the time of the examination and that presence of back pain is confirmed. If the subject expresses interest in learning more about the study, the physician and and/or a research assistant will then explain the study and answer any questions the subject or their family may have.

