16.4 STATISTICAL METHODS

Primary End Point: Average pain intensity over the past 7 days (0–10 numerical rating scale where 0 indicated “no pain” and 10 “worst possible pain”) six weeks and six months after surgery (Dworkin et al., 2005).

Secondary end points: Chronicity of postsurgical pain: Six months after surgery, CPSP will be defined in a dichotomous way (yes/no) as the presence of symptoms 6 months after surgery are reported.

Descriptive statistics (means, SD, medians, n, %) will be calculated in order to present baseline characteristics of the different comparison groups and follow-up measures. To better appreciate the evolution of pain intensity (primary endpoint) during the longitudinal follow-up (baseline to six months after surgery), linear mixed models for repeated measures will be achieved for each of the three comparison schemes described above with the inclusion of the following variables as independent variables to obtain adjusted effects: age, functional outcome score and psychological profile (STAI and PCS scores). This type of analysis is justified by its flexibility in regard to missing data caused by patients lost to follow-up [75] and the possibility to adjust for potential confounders (e.g. patients’ demographics, physical and emotional functioning, clinical characteristics such as medication use or scoliosis parameters). Continuous secondary outcomes will be compared between study groups using similar models. Categorical secondary outcomes such as the presence of chronic postsurgical pain measured 6 months after surgery will be compared between study groups using Chi-square tests. The investigator that will be in charge of the statistical analyses will be blinded to group assignment. As a secondary analysis aiming at understanding the underlying changes over time in QST, pain intensity and catecholamine concentrations will be examined using repeated measures analyses.

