16.5 STRATIFICATION FACTORS

The chosen study design (Figure 7) will test different hypotheses and comparisons between the following groups:

- 1) Placebo group of patients with sub-optimal endogenous inhibitory response vs placebo group of patients with optimal response to test whether patients with inadequate endogenous inhibitory response before surgery are more at risk to develop chronic postsurgical pain (CPSP) than patients with optimal response.
- 2) Clonidine vs placebo group of patients with sub-optimal endogenous inhibitory response to test whether a pharmacological intervention focused on restoring the normal function of the descending inhibitory system reduces the incidence of acute and chronic pain after surgery.

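### The CPSP rule does not separate new or worsened pain from pain present before surgery; this can bias the CPM comparison in either direction and may blunt the clonidine comparison

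*Combined protocol and SAP*

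**What the plan says.** Section 16.2 gives the rule: "CPSP will be defined in a dichotomous way (yes/no) as the presence of symptoms 6 months after surgery is reported". Section 16.4 repeats it almost word for word ("CPSP will be defined in a dichotomous way (yes/no) as the presence of symptoms 6 months after surgery are reported"). Neither section asks that the symptoms be new, worse than before surgery, at the operated site, above an intensity level, or even painful.

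On the test, 16.4 says that "chronic postsurgical pain measured 6 months after surgery will be compared between study groups using Chi-square tests". The covariates and the baseline-to-six-months mixed model in the same section are specified for pain intensity and continuous outcomes, so they do not reach CPSP.

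The question to be answered is in 16.5, item 1: whether placebo patients with sub-optimal inhibition "are more at risk to develop chronic postsurgical pain (CPSP) than patients with optimal response". Section 1 uses the same idea of onset: "between 10 to 20 % of children undergoing surgery will develop chronic postsurgical pain (CPSP").

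On pre-operative pain, Section 4 says "Pain before surgery was reported by 48% of the cohort (n=50") and reports a correlation of 0.50 between pre-operative pain and pain 4–6 weeks after surgery. Section 8.2 has patients told of the study "at the time of the examination and that presence of back pain is confirmed", although 7.1 does not list back pain as an inclusion criterion.

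**The concern.** The hypothesis is about developing a condition after surgery, but the rule counts anyone who has symptoms at 6 months. A patient whose back pain is unchanged, or even improved, is scored as a case. With roughly half of patients in pain beforehand, carried-over pain could supply a large part of the count.

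The two comparisons in 16.5 are exposed differently. Item 1 compares CPM strata, which are patient characteristics and not randomised. Section 4 itself notes that poor CPM is seen in chronic pain disorders, so the sub-optimal stratum may start with more pain. A crude Chi-square could then show that poor CPM predicts CPSP when it only tracks pain already present. Item 2 compares randomised arms within the sub-optimal stratum, so baseline pain is balanced in expectation. What is at stake there is the size and precision of the contrast, not its validity.

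**Working it through.** **The plan's own figure.** Section 16.3 sizes only the primary endpoint: n = 2(1.960 + 1.282)² × (2.0/2)² = 21.01, rounded up to 22 per group, as stated. It gives no rate, effect size or power for CPSP.

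**Inputs from the documents.** Pre-operative pain is 48% (Section 4), group size is 35 and alpha is two-sided 0.05 (16.3).

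**Assumptions.** New-onset CPSP is 20% on placebo vs 10% on clonidine, the two ends of the Section 1 range used as an illustration. A share f of pre-operative pain persists to 6 months, with f = 30%, 50% or 70%. The documents give no persistence rate.

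**Formulas.** Let q = 0.48f be the carried-over share and p the new-onset rate.
- As written: observed rate = q + (1 − q)p.
- New or worsened only: observed rate = (1 − q)p.
- Power: Φ{[|d|√n − 1.96√(2p̄(1 − p̄))] / √(p₁(1 − p₁) + p₂(1 − p₂))}, with n = 35, p₁ and p₂ the two observed rates, d their difference and p̄ their mean.

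**Clonidine comparison, carried-over pain unaffected by treatment** (placebo vs clonidine):

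| f | q | As written | RR | New or worsened | RR | Risk difference, both | Power as written | Power, new or worsened |
|---|---|---|---|---|---|---|---|---|
| 30% | 0.144 | 31.5% vs 23.0% | 0.73 | 17.1% vs 8.6% | 0.50 | 8.6 points | 12% | 18% |
| 50% | 0.240 | 39.2% vs 31.6% | 0.81 | 15.2% vs 7.6% | 0.50 | 7.6 points | 10% | 17% |
| 70% | 0.336 | 46.9% vs 40.2% | 0.86 | 13.3% vs 6.6% | 0.50 | 6.6 points | 8% | 15% |

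Carried-over pain makes up 0.144/0.315 = 46% to 0.336/0.469 = 72% of counted placebo cases. The risk difference is (1 − q) × 10 points under either definition. The broader rule moves the ratio and raises the variance.

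**Clonidine comparison, drug also halves persistence** (f = 50%): the clonidine rate is 0.12 + 0.88 × 0.10 = 20.8%, against 39.2% on placebo. The RR is 0.53 and power is 39%. There is essentially no dilution.

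**CPM comparison** (sub-optimal vs optimal, f = 50%, rule as written). Baseline pain by stratum is assumed.
- 58% vs 38%, true null of 15% in both: 0.29 + 0.71 × 0.15 = 39.65% vs 0.19 + 0.81 × 0.15 = 31.15%, an apparent 8.5 points.
- 68% vs 28%, same null: 43.9% vs 26.9%, an apparent 17.0 points.
- 38% vs 58%, same null: an apparent −8.5 points.
- 58% vs 38%, true 20% vs 10%: 43.2% vs 27.1%, so 10 points appear as 16.1.
- 48% in both, true 20% vs 10%: 39.2% vs 31.6%, so 10 points appear as 7.6.

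Redefining CPSP alone does not fully remove the bias. At 58% vs 38% the null becomes 0.71 × 0.15 = 10.65% vs 0.81 × 0.15 = 12.15%, or −1.5 points. The analysis must therefore account for pre-operative pain as well.

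**Why a minimum change is needed.** With the SD of 2.0 from 16.3 and an assumed baseline-to-6-month correlation r of 0.5–0.9, the SD of change is 2.0√(2(1 − r)) = 2.0 to 0.89. Under no average change, the chance of a rise of at least 1 point is 1 − Φ(0.5/2.0) = 0.40 to 1 − Φ(0.5/0.89) = 0.29. For at least 2 points it is 1 − Φ(1.5/2.0) = 0.23 to 1 − Φ(1.5/0.89) = 0.05.

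**The case against.** A reader might infer that the rule dilutes any drug or CPM effect. The documents do not support that. Dilution of the drug effect needs persisting pain to be unresponsive to clonidine, which no section states. The hypothesis in Section 6 expects less long-term pain without limiting this to new pain. If persistence also falls, the rule as written captures more of the benefit. In the CPM comparison the rule can inflate or create an effect as well as hide one.

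A reader might also set power of 21% (20% vs 10% with all 35 at risk) against the as-written figures. That overstates the loss. Patients whose old pain persists cannot become new cases under any baseline-aware definition, so the fair comparison is 15–18% against 8–12%.

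Nor does 16.5, item 2, name CPSP. It speaks of acute and chronic pain after surgery, for which any pain at 6 months is a defensible measure. Randomisation within CPM stratum keeps that test valid.

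Finally, this is a secondary endpoint for which no power is claimed, and the primary model already starts from baseline.

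All of this stands, and it limits the consequence. It does not supply the missing condition in 16.2 and 16.4, and it does not protect item 1 of 16.5.

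**Conclusion.** The point holds in limited form. The definition mixes new, worsened and pre-existing pain, and the planned test does not separate them.

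The firmest consequence is in the non-randomised CPM comparison, where the result can be biased in either direction. A true null appears as 8.5 points under baseline pain of 58% vs 38% with 50% persistence. The size rests wholly on those assumed figures; the direction depends on how pre-operative pain is distributed across CPM strata.

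For clonidine the test remains valid. Only if persisting pain is unresponsive does the risk ratio move from 0.50 to 0.73–0.86, at a cost of about 6–7 points of power. The absolute difference does not depend on the definition in that case. CPSP is underpowered under either rule, so the gain is in what the result means and not in rescuing power. The primary endpoint and its sample size are unaffected.

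**What to change.** In 16.2 and 16.4, define CPSP as pain at 6 months that is new, or increased over the patient's own pre-operative rating by a pre-stated minimum change. The 2 points that 16.3 already treats as clinically meaningful are a natural choice. State also what rating counts as pain being present.

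Replace the unadjusted Chi-square with an analysis stratified by, or adjusted for, pre-operative pain. Report any pain at 6 months, split by pre-operative pain yes/no, as a sensitivity result. Restricting the analysis to patients without pre-operative pain is not a good substitute: it leaves about 0.52 × 35 = 18 per group and about 13% power for 20% vs 10%.

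The cost is mainly wording, since a pain rating scale is completed at baseline (9.1) and at 6 months (9.5). One check is needed first: 9.1 lists four baseline questions without their content, so confirm that the seven-day average is among them.

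The downside is that patients with severe pre-operative pain have little room to worsen, and unchanged persistent pain counts as no in the main definition. The sensitivity result covers both.
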